2.1.4 STUDY OBJECTIVES

The overall study aim of this study is to provide real world evidence (RWE) on the characteristics, clinical management, treatment outcomes and healthcare resource use of adult patients aged 18 years and older admitted to the hospital for CAP or cSSTI who received Zinforo® in a usual care setting in Europe and Latin America on or before 31-May-2019.

Specific objectives of this study are to analyze for the CAP and cSSTI cohorts:

- Objective 1 “Patient characteristics”: To describe the characteristics of patients hospitalized for CAP or cSSTI who received Zinforo® in a usual care setting in Europe and Latin America on or before 31-May-2019
- Objective 2 “Use of Zinforo”: To describe physicians’ use of Zinforo® in the clinical management of patients hospitalized for CAP or cSSTI in relation to their use of other antibiotics (first-line vs. second-line/salvage, monotherapy vs. combination therapy, empiric vs. definitive therapy)
- Objective 3 “Clinical response”: To estimate the proportion of patients hospitalized for CAP or cSSTI who responded to Zinforo® (clinical response defined as no further intravenous (IV) antibiotic, switch to an oral antibiotic, or IV antibiotic treatment streamlining/de-escalation prior to discharge from the hospital);
- Objectives 4 “Additional clinical outcomes”: To describe the clinical outcomes (eg, hospital readmission, mortality) of patients hospitalized for CAP or cSSTI after starting Zinforo® stratified by clinical response;
- Objective 5 “Treatment modification”: To estimate the proportion of patients hospitalized for CAP or cSSTI who had treatment modification of Zinforo® (defined as switch to another IV antibiotic due to an adverse reaction, drug-drug interaction, insufficient response or a microbiological diagnosis indicating that the pathogen is not susceptible to Zinforo®)
- Objective 6 “Healthcare resource use”: To describe the healthcare resource use of patients hospitalized for CAP or cSSTI after starting Zinforo® stratified by clinical response.

3 HYPOTHESES AND DECISION RULES

This study is purely descriptive in nature and there are no a priori hypotheses specified. Hence, no statistical tests or formal statistical inference will be performed.

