9.4. Data Sources

Data for this study will be collected by a retrospective medical chart extraction from participating sites. The sites will be hospitals in Europe and Latin America that have treated patients with CAP or cSSTI in usual care during the study period. Approximately 600 patient charts will be included in this study from approximately 35-40 sites in Europe and Latin America (15-20 charts per site). Each chart will be retrieved and screened against the inclusion and exclusion criteria. The sites will be responsible for performing all data extraction. For eligible patients, relevant data will be extracted from the hospital medical records from 3-months before the date of the index hospital admission until 30-days after the hospital discharge date or death, whichever occurs first. All data will be entered by sites into electronic case report forms (eCRFs). De-identified data will be collected following the Health Insurance Portability and Accountability Act (HIPAA)-compliant safe harbor approach.³⁴

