7 STATISTICAL METHODOLOGY AND STATISTICAL ANALYSES

7.1.1 SAMPLE SIZE

Given that this study is purely descriptive in nature and since there are no a priori hypotheses specified, a formal sample size calculation is not applicable. It is anticipated that approximately 600 eligible CAP and cSSTI patients from 35-40 participating sites will be sufficient to conduct this study.

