7.1.2 STATISTICAL METHODS

All study outcomes (effectiveness, clinical outcomes, and other endpoints) will be analysed using descriptive statistics to summarize patient and disease characteristics, treatment patterns, and treatment outcomes and health care resource utilisation. Means, standard deviations, medians, minimums and maximums will be provided for continuous variables when performing descriptive analysis of continuous data. Absolute counts and percentages will be provided when performing descriptive analysis of categorical data.

The following variables will be calculated from the information collected in the CRF:

- Body mass index (BMI): Weight(kg) / (Height(cm)*0.01)²
- Geographic region, 2 levels:
 - 1: Europe (France, Greece, Italy, Spain, Russia)
 - 2: Latin America (Brazil, Columbia, Mexico)

Data analyses will be performed separately for the two patient cohorts: CAP and cSSTI. No analyses combining these two patient cohorts will be performed.

Within these patient groups data will be presented in aggregate, as well as stratified by patient and disease characteristics of interest, such as geographic region (see section 4.1.4).

Due to the descriptive nature of the analyses no formal statistical tests will be conducted.. All statistical analyses will be executed using statistical software SAS version 9.4 or later.

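### The two objectives that estimate a proportion (clinical response and treatment modification) will be reported without any measure of uncertainty, and site enters no analysis

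*SAP*

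**What the plan says.** Two of the six specific objectives in SAP 2.1.4 are worded as estimation. Objective 3 is "To estimate the proportion of patients hospitalized for CAP or cSSTI who responded to Zinforo" and Objective 5 is "To estimate the proportion of patients hospitalized for CAP or cSSTI who had treatment modification of Zinforo". The other four are to describe. Protocol section 8 uses the same wording.

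SAP 3 reasons from the absence of hypotheses to the statement that "no statistical tests or formal statistical inference will be performed". SAP 7.1.2 then says: "Absolute counts and percentages will be provided when performing descriptive analysis of categorical data". The shells follow suit: Tables 22 and 24 for CAP and Tables 49 and 51 for cSSTI have columns for n and % only. Neither document mentions a confidence interval or a standard error.

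On size, SAP 7.1.1 says that "a formal sample size calculation is not applicable" and that "approximately 600 eligible CAP and cSSTI patients from 35-40 participating sites will be sufficient to conduct this study". Protocol 9.9 says that feasibility, more than precision, set the target. SAP 7.1.2 analyses CAP and cSSTI separately and never pools them. The protocol abstract says that patient numbers will differ between sites according to past use of the drug. The only groupings by place are region (SAP 4.1.4 and 7.1.2) and a tabulation by country.

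**The concern.** An estimate needs a statement of how precise it is, whether or not anything is tested. Here the step from no hypothesis to no inference removes the interval along with the test.

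Two things are at stake. First, the reader of the report gets a bare percentage for each cohort, and bare percentages again wherever these results are broken down by region, line of treatment or age under SAP 4.1.4, with nothing to show how far they could move by chance. Second, a reader who rebuilds a simple binomial interval from n and N will get one that is too narrow if outcomes are correlated within hospitals. That reader cannot correct it, because no output carries site.

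**Working it through.** **Consistency of the stated figures.** The documents give no precision, power or interval width, so there is no statistical derivation of 600 to reproduce. The planning figures fit together: 600/40 = 15.0 and 600/35 = 17.1 charts per site, inside the 15-20 of Protocol 9.4; 30/600 = 5%, as in SAP 4.1.4.

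**Inputs**
- From the documents: 35-40 sites; stratum floor of 30; illustrative response proportions of 79% (316/398 = 79.4%) for CAP and 85% (550/647 = 85.0%) for skin infection, from the US chart review cited in Protocol section 7.
- Assumed: 300 patients per cohort (range 200-400), a two-sided 95% level, intraclass correlation (ICC) of 0.02 to 0.10, and, for uneven sites, a coefficient of variation (CV) of site size of 0.8. The documents give none of these.

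**Independent patients.** Half-width = 1.96 × √(p(1−p)/n).
- p = 0.79, n = 300: 1.96 × √(0.1659/300) = 4.6 points (Wilson 74.0-83.2%).
- p = 0.85, n = 300: 1.96 × √(0.1275/300) = 4.0 points (Wilson 80.5-88.6%).
- No planning value is given for treatment modification. The widest case, p = 0.50, gives 1.96 × √(0.25/300) = 5.7 points.

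**Clustered patients, equal sites.** Design effect DE = 1 + (m − 1) × ICC, with m = 300/40 = 7.5 to 300/35 = 8.6 patients per site per cohort. The half-width is multiplied by √DE.

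| ICC | DE | Half-width at 79% | Half-width at 85% | √DE |
|---|---|---|---|---|
| 0 | 1 | 4.6 | 4.0 | 1 |
| 0.02 | 1.13-1.15 | 4.9-5.0 | 4.3 | 1.06-1.07 |
| 0.05 | 1.33-1.38 | 5.3-5.4 | about 4.7 | 1.15-1.17 |
| 0.10 | 1.65-1.76 | 5.9-6.1 | 5.2-5.4 | 1.28-1.33 |

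**Uneven sites.** DE = 1 + ((1 + CV²) × m − 1) × ICC. With m = 300/37.5 = 8, CV = 0.8 and ICC = 0.10: DE = 1 + (1.64 × 8 − 1) × 0.10 = 2.21, and the half-widths are 6.9 (79%) and 6.0 (85%).

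**Other cohort sizes** (79% / 85%). With 200 patients: 5.6 / 5.0 if independent, 6.7-6.9 / 5.9-6.0 at ICC 0.10 with equal sites. With 400: 4.0 / 3.5 and 5.5-5.7 / 4.8-5.0.

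**Stratum at the floor of 30.** Wilson limits, with no allowance for clustering: 68.4-93.7% at 85% and 61.6-89.8% at 79%, widths of 93.7 − 68.4 = 25.3 and 89.8 − 61.6 = 28.2 points.

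**The case against.** The strongest reply is that this is a declared descriptive chart review. Protocol 9.2 has most sites abstract every eligible patient, with a cap only at some high-volume sites, and does not describe the sites as randomly drawn. An interval therefore rests on treating these patients as representative of a wider population, and it says nothing about selection through the four-dose rule or the exclusion of charts without outcome information. All of that is true, and the report should say so. It does not remove the need for an interval: the stated aim concerns patients in usual care across Europe and Latin America, and Protocol 9.9 itself worries about generalizability, so the wider population is the intended target.

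It is also fair that clustering adds little here. With about 8 patients per site per cohort, an ICC of 0.05 widens the half-width by less than one point. The larger figures need a high ICC or uneven sites, and 30 is a floor, not an expected stratum size.

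Several stronger readings are tempting and are not supported:
- That the SAP forbids intervals by name. It does not. It excludes formal inference, and the methods and shells show that no interval is planned.
- That the lack of tests or of a power calculation is an error. In a descriptive study it is legitimate.
- That the SAP contradicts the protocol when it says the sample "will be sufficient to conduct this study". That phrase claims no precision, and the protocol openly gives a feasibility basis.
- That a comparison with the US figures of 79% and 85% is planned. Neither document plans one; they are background.

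**Conclusion.** The point stands as a cheap improvement. The plan sets out to estimate two proportions and gives no measure of uncertainty for either, and it leaves site out of every analysis. On an assumed 300 patients per cohort, the unreported half-width at the illustrative response rates is about 4 to 5 points under independence and about 5 to 6 points at ICC 0.10 with equal sites; uneven sites widen it further. At the smallest permitted stratum the interval spans 25 to 28 points. These sizes rest on the assumed split, ICC and site-size variation.

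A reader might infer that ignoring site makes the percentages wrong. It does not bias them in the way they are defined here; it affects how precise they appear.

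**What to change.** In SAP 3 and 7.1.2, keep the exclusion of statistical tests and add two-sided 95% confidence intervals for the clinical response and treatment modification proportions in each cohort, and in any stratum where those proportions are shown. Base the variance on clustering by site, for example with an intercept-only model with robust variance or with survey-type standard errors. Add an interval column to the corresponding shells.

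Two additions are optional: intervals for mortality and readmission, which Objective 4 asks only to describe, and the expected half-widths per cohort and at the 30-patient floor in SAP 7.1.1.

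The cost is a few sentences in the SAP, one extra shell column and a few lines of SAS, with no new data beyond the site identifier. The downside is that stated precision will look less favourable than a bare percentage.

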3.1.1 STATISTICAL HYPOTHESES

Not applicable.

3.1.2 STATISTICAL DECISION RULES

Not applicable.

4 ANALYSIS SETS/POPULATIONS

4.1.1 FULL ANALYSIS SET

The data set will be split by the type of infection (CAP, cSSTI) into two separate analyses sets. The analyses will be performed separately for each of these data sets which will include all subjects with the respective type of infection who are eligible for the study and whose data was entered into the study database (see Section 2.1.1 for eligibility criteria).

4.1.2 SAFETY ANALYSIS SET

Not applicable.

4.1.3 OTHER ANALYSIS SET

No other analysis data sets will be defined.

4.1.4 SUBGROUPS

For selected outcomes, subgroup analyses will be conducted by geography (Europe including Russia, Latin America).

Certain outcomes will be stratified by covariates of interest provided each of the strata exceeds the minimum sample size of 30 patients (5% of total) as specified in the protocol. Covariates for stratified analyses will include:

- For cSSTI patients: Early response within 3 days
- For CAP patients: Early response within 4 days
- Line of treatment
- Age: >65 or ≤65

5 ENDPOINTS AND COVARIATES

5.1.1 EFFECTIVENESS OUTCOMES

5.1.2 TREATMENT RESPONSE TO ZINFORO®

As described in the protocol the clinical response is measured according to the following widely accepted criteria:

- CAP patients: demonstrating clinical stability (defined according to the IDSA guidelines as temperature of ≤ 37.8 C°, heart rate of ≤ 100 beats/min, respiratory rate of ≤ 24 breaths/min, systolic blood pressure of ≥ 90 mmHg, oxygen saturation of $\geq 90\%$, and confusion/disorientation recorded as absent) and clinical improvement (defined as improvement of at least 1 of 4 symptoms present at baseline (i.e., cough, dyspnea, pleuritic chest pain, sputum production) with worsening of none.)
- cSSTI patients: $\geq 20\%$ reduction from baseline infection area and cessation of spread measured by total infection area

Making referencing to the definitions above the following variables will be extracted from charts to assess the clinical response to Zinforo® treatment received during index hospitalization:

- Clinical response, Yes / No, dichotomous from CRF
 - If “Yes”, time to clinical response
- Clinical Cure, Yes / No, dichotomous from CRF
 - If “Yes”, time to clinical cure
- Clinical failure defined as any one of the following:
 - Treatment modification due to adverse event (AE)
 - Time to modification (days from treatment initiation)
 - Drug-drug interaction
 - Insufficient response (followed by switch)
 - Death due to index infection
 - Death due to other cause
 - Relapse or recurrence

For CAP patients specifically, the following effectiveness outcomes will be assessed:

- Time to clinical stability (according to the guidelines from the Infectious Disease Society of America, (IDSA))
- Time to clinical improvement (defined as improvement of at least 1 of 4 symptoms present at baseline)

For cSSTI patients specifically, the following effectiveness outcomes will be assessed:

- Time to $\geq 20\%$ reduction from baseline infection area

PFIZER CONFIDENTIAL

CCI

- Time to cessation of spread measured by total infection area
- Time to cessation of spread measured by infection length and width
 - oral switch,
 - time to symptom resolution,
 - time to clinical stability (Halm criteria),
 - time to oral switch.

The following effectiveness endpoint on early response will be calculated based on the abstracted information:

For cSSTI patients:

- Time to clinical response: Calculated as maximum of:
 - Time to $\geq 20\%$ reduction from baseline infection area
 - Time to cessation of spread measured by total infection area
 - Time to cessation of spread measured by infection length and width
- Early response within 3 days (3 levels):
 - 1: Response according to dichotomous CRF item = “Yes” AND time to response ≤ 3 days
 - 2: Response = “Yes” AND time to response > 3 days
 - 3: No response according to dichotomous CRF item

For CAP patients:

- Time to clinical response: Calculated as maximum of:
 - Time to clinical stability
 - Time to clinical improvement
- Early response within 4 days (3 levels):
 - 1: Response according to dichotomous CRF item = “Yes” AND time to response ≤ 4 days
 - 2: Response = “Yes” AND “Time to response” > 4 days
 - 3: No response according to dichotomous CRF item

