Research question and objectives:	
Study Aim:
 
The overall study aim is to provide real world evidence (RWE) on the characteristics, clinical management, treatment outcomes and healthcare resource use of adult patients aged 18 years and older admitted to the hospital for CAP or cSSTI who received Zinforo® in a usual care setting in Europe and Latin America on or before 31-May-2019.
 
Specific Objectives:
 
 • To describe the characteristics of patients hospitalized for CAP or cSSTI who received Zinforo® in a usual care setting in Europe and Latin America on or before 31-May-2019; • To describe physicians' use of Zinforo® in the clinical management of patients hospitalized for CAP or cSSTI in relation to their use of other antibiotics (first-line vs. second-line/salvage, monotherapy vs. combination therapy, empiric vs. definitive therapy); • To estimate the proportion of patients hospitalized for CAP or cSSTI who responded to Zinforo® (clinical response defined as no further intravenous (IV) antibiotic, switch to an oral antibiotic, or IV antibiotic treatment streamlining/de-escalation prior to discharge from the hospital); • To estimate the proportion of patients hospitalized for CAP or cSSTI who had treatment modification of Zinforo® (defined as switch to another IV antibiotic due to an adverse reaction, drug-drug interaction, insufficient response or a microbiological diagnosis indicating that the pathogen is not susceptible to Zinforo®); • To describe the clinical outcomes (eg, hospital readmission, mortality) of patients hospitalized for CAP or cSSTI after starting Zinforo® stratified by clinical response; • To describe the healthcare resource use of patients hospitalized for CAP or cSSTI after starting Zinforo® stratified by clinical response.
Study design:	Multinational, multicenter observational retrospective cohort study
Population:	The target population is adult patients aged 18 years and older hospitalized for CAP or cSSTI who received intravenous (IV)

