8. RESEARCH QUESTION AND OBJECTIVES

Study Aim:

The overall study aim is to provide real world evidence (RWE) on the characteristics, clinical management, treatment outcomes and healthcare resource use of adult patients aged 18 years and older admitted to the hospital for CAP or cSSTI who received Zinforo[®] in a usual care setting in Europe and Latin America on or before 31-May-2019.

Specific Objectives:

- To describe the characteristics of patients hospitalized for CAP or cSSTI who received Zinforo® in a usual care setting in Europe and Latin America on or before 31-May-2019.
- To describe physicians' use of Zinforo® in the clinical management of patients hospitalized for CAP or cSSTI in relation to their use of other antibiotics (first-line vs. second-line/salvage, monotherapy vs. combination therapy, empiric vs. definitive therapy).
- To estimate the proportion of patients hospitalized for CAP or cSSTI who responded to Zinforo® (clinical response defined as no further intravenous (IV) antibiotic, switch to an oral antibiotic, or IV antibiotic treatment streamlining/de-escalation prior to discharge from the hospital).
- To estimate the proportion of patients hospitalized for CAP or cSSTI who had treatment modification of Zinforo® (defined as switch to another IV antibiotic due to an adverse reaction, drug-drug interaction, insufficient response, or a microbiological diagnosis indicating that the pathogen is not susceptible to Zinforo®).
- To describe the clinical outcomes (eg, hospital readmission, mortality) of patients hospitalized for CAP or cSSTI after starting Zinforo® stratified by clinical response.
- To describe the healthcare resource use of patients hospitalized for CAP or cSSTI after starting Zinforo® stratified by clinical response.

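### SAP 5.1.2 credits the protocol with response rules that the protocol does not contain, and the table shells do not derive response as Objective 3 defines it

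*SAP*

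**What the plan says.** Protocol section 4 sets the objective "To estimate the proportion of patients hospitalized for CAP or cSSTI who responded to" Zinforo, and section 8 gives the definition: "clinical response defined as no further intravenous (IV) antibiotic, switch to an oral antibiotic, or IV antibiotic treatment streamlining/de-escalation prior to discharge". SAP 2.1.4 repeats it as Objective 3, beginning "clinical response defined as no further intravenous (IV) antibiotic, switch to an oral antibiotic". All three places describe what happened to the antibiotic course.

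SAP 5.1.2 sets a different standard under the words "As described in the protocol the clinical response is measured according to the following widely accepted criteria". CAP patients must meet a list of IDSA stability thresholds and improve in at least one of four baseline symptoms with none worsening. For cSSTI the rule is at least a 20% "reduction from baseline infection area and cessation of spread measured by total infection area". The section continues "Making referencing to the definitions above the following variables will be extracted from charts to assess the clinical response" and lists first "Clinical response, Yes / No, dichotomous from CRF". The early-response categories later in 5.1.2 are built on that item. SAP 7.1.4 says only that the proportions with response, cure and failure will be summarised.

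Tables 22 (CAP) and 49 (cSSTI) carry the response row. Tables 10 and 11 (CAP) and 37 and 38 (cSSTI) split resource use and cost by responder status. Table numbers here are those in the body of the SAP.

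**The concern.** Two different constructs share the name clinical response, and the SAP presents the second as the protocol's own. A reader of Tables 22 and 49 would take the response row for the proportion that the protocol set out to estimate, although 5.1.2 ties that row to other criteria.

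The study has no hypothesis tests, so its estimated proportions are its results, and their definitions carry the weight. Objective 3 is one of six objectives. Objectives 4 and 6 describe clinical outcomes and resource use by clinical response, so the choice of classification reaches those as well.

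**Working it through.** The plan gives no figure to reproduce and no arithmetic applies beyond counting. The check sets the texts side by side.

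**Step 1. Are the SAP 5.1.2 criteria in the protocol?**

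| SAP 5.1.2 rule | Protocol text |
|---|---|
| CAP: stability thresholds | Halm criteria named in section 4 (an option in a response-definition variable) and section 9.3 (a time variable); no thresholds given |
| CAP: one of four symptoms improved, none worse | Absent; 9.3 lists only time to symptom resolution |
| cSSTI: area reduction of at least 20% | Absent |
| cSSTI: cessation of spread | Absent |

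Three of the four rules are missing. For the fourth, neither document states the Halm thresholds, so agreement or disagreement cannot be judged.

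**Step 2. Does the SAP derive the Objective 3 response?**

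| Objective 3 component | Row in Table 22 | Row in Table 49 | Elsewhere in the SAP |
|---|---|---|---|
| No further IV antibiotic | No | No | Tables 27 and 54: any later antibiotic, yes/no, not limited to IV |
| Oral switch | No | No | 5.1.2, under the cSSTI list only, with "time to oral switch"; route in Tables 27 and 54 |
| IV de-escalation | No | No | Only in the wording of Objective 3 |

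That is 0 of 3 in each response table, and no row for the composite. Protocol 9.3 names six response variables. Four appear in SAP 5.1.2, nested under the cSSTI items. The two left out are the response definition and treatment de-escalation.

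**Step 3. Can Tables 27 and 54 supply the proportion?** They give later antibiotic use, route and reason for switch as separate margins.

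- A patient recorded with no later antibiotic may have recovered or died.
- A patient switched to oral therapy counts as having a later antibiotic.
- Route is summarised across all lines, not as a switch per patient.
- Seven switch reasons are listed (lack of efficacy, side effect, interaction, susceptibility or pathogen result, renal impairment, other, unknown). None identifies de-escalation separately.

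The composite cannot be rebuilt from these margins.

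**Step 4. Can the two definitions disagree for one patient?** Yes, in both directions. A cSSTI patient moved to oral therapy before a 20% reduction is recorded meets Objective 3 but not 5.1.2. A CAP patient who stabilises and improves, then changes to another IV drug because of an adverse reaction, meets the 5.1.2 response criteria. Unless the change counts as de-escalation, that patient does not meet Objective 3.

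**Step 5. Which definition forms the responder groups in Tables 10, 11, 37 and 38?** None is stated.

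**The case against.** The strongest objection is that the CRF is not available. Protocol section 4 lists a response-definition variable with oral switch among its options, so a site's yes could rest on exactly what Objective 3 asks for. The link to the SAP criteria is a single loosely worded sentence. This stands as a limit: the conflict is in the written definition, and what sites recorded is unknown.

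Three further points narrow the finding:

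- The protocol is not silent on clinical signs, since it names Halm criteria and symptom resolution. A reader might infer that the SAP stability thresholds depart from the protocol; the documents do not show that.
- De-escalation driven by culture results could be coded under the susceptibility reason or under other. A reader might infer that it was not captured at all. The supportable statement is that the tables do not identify it separately.
- Oral switch is listed in SAP 5.1.2 only under cSSTI, so its absence from the CAP table does not contradict that list. The nesting may be an editing or layout slip.

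Protocol 9.7 lets the SAP modify the plan, but 5.1.2 declares no modification; it claims agreement. The same section sends major changes of primary endpoint definitions to a protocol amendment. A reader might infer that an amendment is therefore mandatory. No single primary endpoint is named, so that is open.

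That the study is descriptive lowers the stakes of any one result but does not make the definition optional.

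**Conclusion.** The point holds as a conflict of written definitions. The attribution to the protocol is wrong for the symptom, area and spread rules. The SAP's response row is tied to criteria other than those in its own Objective 3, and no shell derives the antibiotic-course response or any of its three components in the response tables. The responder groups behind the resource-use and cost tables are undefined.

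The effect on the reported proportion cannot be sized, because neither document shows how often the two definitions disagree.

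Two stronger readings go too far. One is that the reported proportion will certainly differ from the Objective 3 proportion, which would require the CRF and its completion instructions. The other is that Tables 10, 11, 37 and 38 certainly use the CRF yes/no item; that is likely, but the SAP does not say so.

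The conclusion rests on the supplied text of both documents. The protocol's 72-hour strata against the SAP's 4-day cut for CAP, and the different cSSTI table numbers in the SAP list of tables, are separate and minor.

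**What to change.** 1. In SAP 5.1.2, remove the attribution to the protocol and report those criteria under a separate name. Record them as a change from the protocol, and decide and state whether Protocol 9.7 requires an amendment, given that no single primary endpoint is named.
2. Add to Tables 22 and 49 the Objective 3 response and its three components, derived per patient from the post-Zinforo antibiotic, route, oral-switch and de-escalation data. Do not count a patient who died on Zinforo as a responder through having no further IV antibiotic: Protocol 9.3 and SAP 5.1.2 both class death as clinical failure. If the CRF has no de-escalation field, state that this component cannot be derived.
3. State which classification defines responders in Tables 10, 11, 37 and 38. Tabulate the response-definition field if it was collected.
4. State whether the response and failure rows can overlap, for example when a responder relapses.

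The cost is some rewording, a few table rows and one check of the CRF, with no new data collection. The report will then carry two response proportions per cohort, and the difference between them will need a sentence of explanation.
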